Study Population	Enrollment in the study will be available to all subjects who start therapy with the Control-IQ System once the Institutional Review Board (IRB) approval is received and the subject meets the indications for use and the study eligibility criteria. As specific target subgroups are filled, we may elect to only

	enroll subjects whose subgroup recruitment goals have not been completed. Electronic informed consent will be required from all subjects prior to participation in the study.
Number of Subjects	
The study will recruit a minimum of 2,063 subjects. For the primary safety endpoints, the projected total recruitment sample size of at least 2,063 subjects (including 25% attrition) would provide 80% power with a 2-sided type 1 error rate of 5%. With attrition, it is expected that 1,547 subjects will complete the study. Recruitment goals for study subgroups will include:
 
 
• At least 385 subjects in the 6 to 13 year-old cohort, and at least 328 subjects in the 14 to <math>\leq</math>18 year-old cohort. Depending on the rate of recruitment in these two age groups, the balance of the total sample will be recruited from the <math>></math>18 year-old subgroup.
 
• Details on subgroup enrollment targets can be found on page 23 “Determination of Sample Size”
 

Number and Location of Sites	All data for this study will be collected remotely, with no live clinical visits conducted. Data will be collected electronically, via surveys and automated uploads of pump and CGM data, as well as via in- and out-bound telephone calls and SMS messaging.

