## SUBJECT SELECTION

### Subject Population

**Inclusion Criteria:** Patients must consent to meet the following criteria in order to be enrolled in the study:

- 1) Patients with self-reported type 1 diabetes who have been prescribed the Control-IQ system.
- 2) At least 6 years of age
- 3) Using Humalog or Novolog insulin
- 4) For females, not pregnant or planning pregnancy in the next 12 months.
- 5) Agreement to use the t:slim X2 with Control-IQ technology, and to continue use for at least 12 consecutive months after study enrollment.
- 6) Agree to provide HbA1c result, obtained within the 6-month period prior to enrollment.
- 7) Ability to respond to alerts and alarms, and to provide basic diabetes self-management.
- 8) Patients who reside full-time in the United States.
- 9) Willingness to download the t:connect Mobile application to their Smartphone and keep it active throughout the study. Patients unable to use t:connect mobile application must be willing to manually upload their insulin pump data to t:connect every three months and at the completion of the study.
- 10) Subject has read, understood and agreed to participate in the study, and has electronically signed the Informed Consent Form (ICF).

**Exclusion Criteria:** Patients with the following characteristics will not be considered candidates for the study:

- 1) Self-reported type 2 diabetes
- 2) < 6 years of age
- 3) Use of any glucose-lowering therapy other than Humalog or Novolog insulin
- 4) Inability to respond to alerts and alarms, or to provide basic diabetes self-management.
- 5) Pregnancy
- 6) Subjects who have not signed the ICF.

Any discrepancy in the above criteria between data in CRM and subject's self-reported criteria will be electronically alerted to study staff. Study staff will then clarify inclusion/exclusion criteria prior to enrolling the subject.

Over the course of the study as specific participant recruitment subgroups are filled, we may enroll subjects whose subgroup goals have not been completed and elect to exclude otherwise applicable participants.

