A separate power analysis for the 14-18 age group used an overall DKA incidence rate of 14.2 events/100PY. Results indicated that a sample size of 328 individuals with T1D between the ages of 14-18 would provide 80% power with a type 1 error rate (two-sided) of 5% to detect a difference, if there is one, between the expected DKA rate (14.2) and the proposed study sample DKA event rate. Of the overall sample of 1,282 subjects, at least 328 subjects will be 14-18 years old to provide sufficient power to detect risk of DKA in this younger age group.

A separate power analysis for the 6-13 year old group used an overall DKA incidence rate of 13.2 events/100PY, which is a weighted average of both MDI and pump users (since pump users were overrepresented in this age group). Results indicated that a sample size of 77 individuals with T1D between the ages of 6-13 would provide 80% power with a type 1 error rate (two-sided) of 5% to detect a difference, if there is one, between the expected DKA rate (13.2/100PY) and the proposed study sample DKA event rate. In addition to the previously determined sample, at least 77 subjects will be 6-13 years old to provide sufficient power to detect risk of DKA in this younger age group.

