### ***Step 3 – Final sample size determination***

The projected total recruitment sample size of at least 2,063 subjects (including attrition) would provide 80% power with a 2-sided type 1 error rate of 5%. Considering the 25% attrition mentioned above, it is the expectation to have 1,354 subjects complete the study. Recruitment goals for study subgroups will include:

- At least 385 subjects in the 6 to 13 year old cohort, and at least 328 subjects in the 14 to  $\leq$  18 year old cohort. Depending on the rate of recruitment in these two age groups, the balance of the total sample will be recruited from the  $>18$  year old subgroup.
- Of the 6-13 year old cohort:
  - At least (n=163) will be 6-9 years old, as recently published data of 30 children age 6-9 shows successful use of Control-IQ technology (10).
  - At least 25% (n=96) will have a baseline A1c  $\geq$  8.5%
  - At least 25% (n=96) will be pump naïve
  - At least 5% (n=18) will be CGM naïve. This percentage is based on clinical evidence of high baseline CGM use in this age group, and recently published data of 40 CGM naïve children who successfully used Control-IQ

technology (10). With the availability of this data from these 40 participants, recruitment goals for the CGM naïve cohort of children in CLIO was reduced to 18 participants.

- Of the >14 year old cohort,
  - Approximately 677 subjects each in the pump user and pump naïve subgroups at baseline.
  - Approximately 270 subjects that are CGM naïve (defined as not using CGM in the 30 days prior to enrollment).
  - Approximately 681 subjects (33% of total sample) with HbA1c  $\geq 8.5\%$  and 681 subjects (33% of total sample) in the <8.5% subgroup

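### The 14–18 recruitment goal of 328 is the un-inflated sample size for 80% DKA power, so that power is not delivered if enrolment stops at the goal and 25% are lost

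*Combined protocol and SAP*

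**What the plan says.** Determination of Sample Size, Step 2, gives the DKA calculation for adolescents at a reference rate of 14.2 per 100 patient-years and two-sided alpha of 5%: "Results indicated that a sample size of 328 individuals with T1D between the ages of 14-18 would provide 80% power". It places these participants inside the overall DKA power-analysis sample: "Of the overall sample of 1,282 subjects, at least 328 subjects will be 14-18 years old to provide sufficient power".

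Step 3 and the Protocol Synopsis (Number of Subjects) then list recruitment goals: "At least 385 subjects in the 6 to 13 year old cohort, and at least 328 subjects in the 14 to" 18 years. The balance of the total is to come from adults.

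Attrition appears at the level of the total. The Synopsis says "the projected total recruitment sample size of at least 2,063 subjects (including 25% attrition) would provide 80% power", and then "With attrition, it is expected that 1,547 subjects will complete the study". Step 3 cites the same 25% with a different result: "Considering the 25% attrition mentioned above, it is the expectation to have 1,354 subjects complete the study".

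Two places allow enrolment to be restricted. The Synopsis (Study Population) says "As specific target subgroups are filled, we may elect to only" enrol people whose subgroup goals are still open. Subject Population says "we may enroll subjects whose subgroup goals have not been completed and elect to exclude otherwise applicable participants".

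Four other provisions bear on the point:
- Data collected before withdrawal are kept and analysed (Subject Withdrawal or Termination).
- The primary outcome is a rate per 100 patient-years (Primary Outcome).
- The test is a one-sample, two-tailed exact binomial test at 0.05 (Statistical Analysis).
- A participant with no Control-IQ data downloaded by 120 days after the baseline survey is a screen failure (Duration of therapy and follow-up).

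**The concern.** A number required for analysis and a number to be recruited should differ by the attrition allowance. Here they are the same, in a plan that expects to lose a quarter of its participants. A team that follows the protocol exactly can recruit 328 adolescents, close the subgroup, and finish with less information than Step 2 says it needs.

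Step 2 gives the purpose of the 328 as adequate power to detect DKA risk in this age group, and DKA is a primary safety endpoint. The success criterion is that incidence is no higher than in the literature. With lower power, a true increase among adolescents is easier to miss, and a reader of a non-significant result would credit it with 80% sensitivity that it may not have.

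**Working it through.** **Inputs from the documents.** Reference DKA rate 14.2/100 PY, so p0 = 0.142; required n = 328; two-sided alpha 0.05; power 80% (Step 2). Goal 328 (Synopsis, Step 3). Attrition 25% (Synopsis). Severe hypoglycaemia (SH) requirement for ages 14–18: 231 (Step 1). Printed DKA rate for pump users aged 13–17: 9/100 PY (Primary Outcome table).

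**The plan's own figure.** The 328 cannot be reproduced directly, because Step 2 gives no alternative rate. With the normal approximation, n = [1.96·√(p0(1−p0)) + 0.842·√(p1(1−p1))]² / (p1−p0)². An alternative of 9/100 PY gives 317; 328 corresponds to about 9.1 (decrease) or 19.8 (increase). With the equal-tailed exact binomial test, power is 80% at n = 328 for p1 = 0.0919 or 0.2001.

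**Where attrition is applied.**
- Total: 2,063 × 0.75 = 1,547, as the Synopsis states.
- Ages 6–13: 288 / 0.75 = 384, against a goal of 385. This is consistent with an allowance, although the derivation of 385 is not given.
- Ages 14–18: 328 / 0.75 = 437.3, or 438. The goal is 328.
- The balance, 2,063 − 385 − 328 = 1,350, is assigned to adults, so nothing in the total tops up the adolescents.

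**What 328 recruits yield at 25% loss.**
- Completers: 328 × 0.75 = 246, which is 82 fewer than 328.
- Person-years, if the 82 dropouts average half a year (assumption): 246 + 82 × 0.5 = 287.

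**Illustrative power.** Exact binomial test, p0 = 0.142, two-sided 0.05. Person-years are treated as the binomial n, which is a simplification. The two usual exact constructions are shown where they differ.

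| Alternative (per 100 PY) | n = 328 | n = 287, equal-tailed | n = 287, minimum-likelihood | n = 246, both |
|---|---|---|---|---|
| 9.19 (back-solved) | 80% | 74% | 68% | 67% |
| 20.01 (back-solved) | 80% | 72% | 76% | 66% |
| 9 (printed rate) | 83% | 78% | 72% | 71% |

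Exact power moves in steps, so a single n can mislead. Over every n from 240 to 287, under all three alternatives and both constructions, power never exceeds 78%.

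**SH in the same cohort.** 246 > 231, so the SH requirement is still met at 25% loss.

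**The case against.** **The shortfall is conditional.** The goal is a floor. The plan says enrolment may be restricted, not that it will be, and the adult balance depends on how fast the younger groups recruit. Recruiting 438 or more would remove the problem. This stands, and the point is limited to enrolment stopping at or near 328. But nothing requires more than 328.

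**Some goals may be on an evaluable scale.** The pump-user and pump-naïve goals for the older cohort are 677 + 677 = 1,354, the un-inflated SH sample, so attrition might be carried only in the 2,063. That is possible, but Step 3 calls the whole list recruitment goals, and a reader cannot tell.

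**The size of the loss cannot be fixed.** This also stands. Alternatives back-solved to 80% at 328 must give less at a materially smaller n, and the printed 9/100 PY starts with a little slack (83%). The figures show scale only.

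**Attrition among counted participants may be below 25%.** The revision history reports that about 24% had completed the baseline questionnaire without progressing to the Month 1 survey, and gives this as the reason for the 120-day rule. If the 25% includes those screen failures, the loss among those counted is smaller. The plan does not say.

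**The consequence is limited.** No separate success criterion is set for DKA in ages 14–18. That is correct, but Step 2 does claim power for this group.

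**A stronger reading that does not hold.** A reader might divide Step 3's 1,354 by 2,063, infer a 34% loss, and conclude that SH also falls short (about 215 of 328, below 231). The documents do not support this. Step 1 places the 6–13 cohort in addition to the overall SH sample of 1,354. The match with 677 + 677, and 1,698 (Study Design) + 288 + 77 = 2,063, both suggest that 1,354 excludes that cohort. The ratio would then mix two populations. On a matched denominator the loss is 1 − 1,354/1,698 = 20%, or 1 − 1,354/1,678 = 19% (where 1,678 = 2,063 − 385). This is an inference, but it is enough to rule out a claimed SH shortfall.

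**Conclusion.** The point holds in conditional form. The same 328 serves as the number needed for 80% DKA power in ages 14–18 and as the number to recruit, with no attrition allowance shown. If the subgroup closes at 328 and 25% are lost, the stated 80% is not delivered.

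The conclusion rests on enrolment stopping at the goal, on the 25% applying to counted participants, and, for the 287 figure, on dropouts averaging half a year. The direction does not depend on the unstated alternative rate, apart from small step effects; the power values do.

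The effect is confined to DKA in one age subgroup. SH there is covered at the stated loss, and the overall comparison does not depend on it. The mismatch between 1,354 and 1,547 expected completers is a separate inconsistency and does not enlarge this point.

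**What to change.** In the Synopsis (Number of Subjects) and in Steps 2 and 3 of Determination of Sample Size:

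1. State that 328 is the number analysed, or the person-years, needed for 80% DKA power in ages 14–18, and that 328 recruited gives less than 80% after 25% attrition.
2. Restate the 14–18 DKA power, computed by the sponsor with the planned exact test at the expected person-years. Give the alternative rate and the denominator (completers or person-years). Possible wording for Step 3: *At least 328 participants aged 14 to 18 will be recruited; after 25% attrition about [x] person-years are expected, giving [y]% power for DKA against an alternative of [z] per 100 PY.*
3. Say whether the 25% includes the 120-day screen failures.
4. Separately, reconcile 1,354 expected completers (Step 3) with 1,547 (Synopsis), naming the population each refers to.

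The cost is wording and one power calculation. The total, the subgroup goals and data collection can stay as they are. The power values shown here are illustrative and should not be copied into the protocol.

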## **Statistical Analysis**

Descriptive statistics will be used to describe outcomes vs. a comparator group. The Comparator Group will be determined using evidence from a systematic literature review examining MDI, insulin pump therapy (IPT) and sensor augmented pump (SAP) use in patients with type 1 diabetes. Studies published since January, 2020 will be included in the analysis. This will establish the baseline sample representation and outcome metrics. Users of automated dosing systems, including low glucose suspend, predictive low glucose suspend (such as Basal-IQ technology) will not be analyzed as part of the Comparator group.

The publications included in the literature review have been identified to represent the typical population of people with type 1 diabetes, and include sample populations that mirror those described above in the target population for this study, including:

- Children age 6 years old and older
- Adolescents age 14-18 years old
- Adults >18 years old
- Patients with pump experience
- Pump naïve patients
- Patients with CGM experience
- CGM naïve patients
- Wide range of baseline HbA1c values

Primary endpoints, the risk of AE (DKA, SH), represented as risk ratio per 100 patient years, will be compared using a single sample two-tailed exact binomial test (alpha=0.05) to the expected values as extracted in the literature review. Effect size will be defined as the absolute difference in risk ratios.

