Statistical Analysis	
Descriptive statistics will be used to evaluate outcomes vs. a comparator group. The Comparator Group will be determined using evidence from a systematic literature review examining MDI, insulin pump and sensor augmented pump (SAP) use in patients with type 1 diabetes. Primary endpoints, the risk of AE (DKA, SH), represented as risk ratio per 100 patient years, will be compared using a single sample two-tailed exact binomial test (alpha=0.05) to the expected values as extracted in the literature review. Effect size will be defined as the absolute difference in risk ratios. The safety of automatically populating CGM readings into the bolus calculator will be analyzed by correlating reported AEs, calculator usage data and CGM readings to understand if the bolus calculator may have caused the AE. This analysis will isolate AEs where three consecutive CGM readings <math>\leq 54</math> mg/dL, or <math>\geq 250</math> mg/dL existed within five hours after a correction bolus was given using an automatically populated CGM reading. Boluses using automatically populated CGM values <math>\geq 250</math> mg/dL will be analyzed and evaluated separately from boluses given for lower glucose values.
 
Secondary endpoints will be calculated as means/medians as appropriate based on data extracted from the Tandem t:connect web application and patient reported outcomes. Sensor-glucose concentrations will be analyzed per recent international consensus guidelines, to include time in target range 70-180 mg/dL, time <math>> 180</math> mg/dL, time <math>> 250</math> mg/dL, time <math>< 70</math> mg/dL, time <math>< 54</math> mg/dL.
 
Outcomes will be analyzed quarterly and tabulated using standard statistical tools such as R and Python.

----------------------	--

The study will be conducted and documented in accordance with the US Federal and Local requirements for post-market human clinical studies, the protocol, and the stipulations of the clinical trial agreement.

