## **STATISTICAL CONSIDERATIONS**

### **Determination of Sample Size**

The approach to sample size and statistical analyses are summarized below. A detailed statistical analysis plan will be written and finalized prior to the first tabulation of data. In order to determine the incidence rates on which the power analyses were based, Tandem conducted a literature review (see Attachment 1 for methodology). Ranges of event rates reported in the literature for both severe hypo and DKA in patients with T1D are very broad; 0-100 events/100PY for severe hypoglycemia, and 0.4 – 26 events/100 PY for DKA (see Table 1, Attachment 1). Therefore, for purposes of power analyses for the proposed study, we used event rates from a recently published study using a large Type 1 Diabetes Exchange cohort (Foster et al, 2019). This study used a similar design as our approved post-market study, the subjects represent our intended use population, and the event rates reported in the Foster study fall within the broader rates found in the extensive body of literature reviewed.

Sample size was determined in 3 steps:

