#### *Step 1 – Power analysis for severe hypoglycemia (SH)*

An overall incidence rate of 25.35 events per 100 patient years (PY) was used in the power analysis for severe hypoglycemia. We calculated that a sample size of 1,354 individuals with T1D would provide 80% power with a type 1 error rate (two-sided) of 5% to detect a difference, if there is one, between the expected SH rate (25.35) and the proposed study sample SH event rate.

A separate power analysis for the 14-18 age group used an overall SH incidence rate of 19.5 events/100PY. Results indicated that a sample size of 231 individuals with T1D between the ages of 14-18 would provide 80% power with a type 1 error rate (two-sided) of 5% to detect a difference, if there is one, between the expected SH rate (19.5) and the proposed study sample SH event rate. Of the overall sample of 1,354 subjects, at least 231 subjects will be 14-18 years old to provide sufficient power to detect risk of SH in this younger age group.

A separate power analysis for the 6-13 year old group used a SH incidence rate of 21.9 events/100PY, which is a weighted average of both MDI and pump users (since pump users were overrepresented in this age group). Results indicated that a sample size of 288 individuals with T1D between the ages of 6 and 13 would provide 80% power with a type 1 error rate (two-sided) of 5% to detect a difference, if there is one, between the expected SH rate (21.9) and the proposed study sample SH event rate. In addition to

the overall sample, at least 288 subjects will be 6-13 years old to provide sufficient power to detect risk of SH in this younger age group. *Step 2 – Power analysis for diabetic ketoacidosis (DKA)*

An overall incidence rate of 11.03 events per 100 patient years was used in the power analysis for DKA . We calculated that a sample size of 1,282 individuals with T1D would provide 80% power with a type 1 error rate (two-sided) of 5% to detect a difference, if there is one, between the expected DKA rate (11.03/100 PY) and the proposed study sample DKA event rate.

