## **Primary Outcome**

Incidence rate/100 patient years for both severe hypoglycemia (SH) and diabetic ketoacidosis (DKA).

**Success Criteria/Goal:** Study participants will not experience a higher incidence of SH or DKA than incidence rates reported in the literature from analyses of similar populations. Overall outcomes will be compared to data below, derived from a recently published study using a large Type 1 Diabetes Exchange cohort (Foster et al., 2019). This study used a similar design as our postmarket study proposed here, the subjects represent our intended use population, and the event rates reported in the Foster study fall within the broader rates found in the extensive body of literature reviewed.

SH Incidence Rates (all ages)		SH Incidence Rates in Children			SH Incidence Rates in Adults	
All ages (13-93)			Ages 6-12	Ages 13-17	Ages 18-93	
All insulin delivery	25/100 PY	All insulin delivery	22/100 PY	20/100 PY	All insulin delivery	30/100 PY
MDI	37/100 PY	MDI	28/100 PY	34/100 PY	MDI	38/100 PY
IPT	23/100 PY	IPT	16/100 PY	13/100 PY	IPT	27/100 PY
DKA Incidence Rates (all ages)		DKA Incidence Rates in Children			DKA Incidence Rates in Adults	
All ages (13-93)			Ages 6-12	Ages 13-17	Ages 18-93	
All insulin delivery	11/100 PY	All insulin delivery	13/100 PY	14/100 PY	All insulin delivery	9/100 PY
MDI	17/100 PY	MDI	22/100 PY	25/100 PY	MDI	13/100 PY
IPT	7/100 PY	IPT	5/100 PY	9/100 PY	IPT	7/100 PY

The full literature review can be found in Attachment 1 of this protocol.

The safety of automatically populating CGM readings into the bolus calculator will be analyzed by correlating reported AEs, calculator usage data and CGM readings to understand if the bolus calculator may have caused the AE. This analysis will isolate AEs where three consecutive CGM readings  $\leq 54$  mg/dL, or  $\geq 250$  mg/dL existed within five hours of receiving a correction bolus using an automatically populated CGM reading. All CGM readings within 5 hours after the bolus is given will be evaluated. In addition, correction boluses using automatically populated CGM values  $\geq 250$  mg/dL will be analyzed and evaluated separately from boluses given for lower glucose values.

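### The primary SH and DKA endpoints are event rates, but the named test is a one-sample exact binomial with no defined trial, so its error rate and even its conclusion are left open

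*Combined protocol and SAP*

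**What the plan says.** - Primary Outcome defines the endpoint as "Incidence rate/100 patient years for both severe hypoglycemia (SH) and diabetic ketoacidosis (DKA"). The success goal beneath it reads "Study participants will not experience a higher incidence of SH or DKA than incidence rates reported in the literature".
- Determination of Sample Size states the nulls in the same unit: "An overall incidence rate of 25.35 events per 100 patient years (PY) was used in the power analysis for severe hypoglycemia" (Step 1) and "An overall incidence rate of 11.03 events per 100 patient years was used in the power analysis for DKA" (Step 2). Their source is given there: "we used event rates from a recently published study using a large Type 1 Diabetes Exchange cohort".
- Statistical Analysis then sets the test. The endpoints, described as the risk of an adverse event, are "represented as risk ratio per 100 patient years, will be compared using a single sample two-tailed exact binomial test (alpha=0.05"). The Synopsis repeats it: they "will be compared using a single sample two-tailed exact binomial test (alpha=0.05) to the expected values as extracted in the literature review".
- The effect measure is given as: "Effect size will be defined as the absolute difference in risk ratios".
- A form is completed for each verified adverse event (Observation and Recording of Adverse Events), so repeat events are captured. Data from subjects who withdraw stay in the analysis (Subject Withdrawal or Termination), so exposure is unequal. AE incidence is surveyed monthly (Synopsis, Periodic Data Collection procedures).
- No section defines the trial, the success, the treatment of repeat events or the treatment of partial follow-up.

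**The concern.** An event rate per patient-year is not a probability. One patient can have several events, and a count over person-time has no fixed number of yes/no trials. To run the named test, someone must choose a trial, and three choices are open:

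- (a) each patient-year is a trial and each event a success;
- (b) each person is a trial and having at least one event is the success, which the word risk suggests;
- (c) each patient-month is a trial, with the null rate divided by 12, which the monthly surveys would support.

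These are different tests. (a) uses a variance that is too small for a count. (b) compares a proportion of persons with a rate of events. (c) is close to a Poisson test but ignores clustering within a patient.

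This is the only inferential test named for SH and DKA, in a study whose main purpose is safety. Reading (b) errs towards the success goal: it can report a lower rate that does not exist and miss a real excess. Outcomes are also analysed quarterly, so an open choice could be settled after data have been seen. Finally, a single-arm rate has no risk ratio per 100 patient-years, and a difference of risk ratios is not an effect measure for it.

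**Working it through.** **The plan's own figures.** 1,547/0.75 = 2,063, so the Synopsis recruitment figure reproduces with 25% attrition. The 1,354 (SH) and 1,282 (DKA) cannot be reproduced, because neither the alternative rate nor the test behind them is stated.

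**Inputs.** N = 1,547 completers (Synopsis, Number of Subjects), one year each. Benchmark rate λ0 = 0.2535 (SH) and 0.1103 (DKA) per patient-year. Two-sided α = 0.05, exact binomial by the minimum-likelihood rule. Events are Poisson, or negative binomial with variance μ(1 + kμ) per patient. The dispersion k is an assumption, since the documents give none.

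**Why reading (a) is too liberal.** For SH the binomial SD of the total is √(1,547 × 0.2535 × 0.7465) = 17.1, while the Poisson SD is √(1,547 × 0.2535) = √392.2 = 19.8. For DKA the two are √(1,547 × 0.1103 × 0.8897) = 12.3 and √170.6 = 13.1.

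**Rejection regions (total events) and true size when the rate equals the benchmark:**

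| Reading | Endpoint | Reject if | Poisson | k=1 | k=2 | k=4 |
|---|---|---|---|---|---|---|
| (a) patient-years | SH | ≤358 or ≥427 | 8.6% | 12.5% | 16.2% | 22.6% |
| (a) patient-years | DKA | ≤146 or ≥196 | 6.1% | 7.5% | 8.9% | 11.8% |
| (c) patient-months, n = 18,564 | SH | ≤353 or ≥431 | 5.2% | 8.2% | 11.3% | 17.0% |
| (c) patient-months, n = 18,564 | DKA | ≤145 or ≥197 | 5.1% | 6.4% | 7.7% | 10.4% |

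With the 1,354 completers given in Step 3, reading (a) under Poisson gives 8.9% and 6.0%.

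**Reading (b).** Under Poisson, P(at least one event) = 1 − exp(−λ), which is 22.4% for SH and 10.4% for DKA at the benchmark. Testing these against 0.2535 and 0.1103 declares the rate lower with probability 77% (SH) and 10% (DKA). If the benchmark instead counted persons affected per year, the size would be 4.7% for both.

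**Power to flag a real excess as higher.** The comparison is with a rate test using robust variance. By normal approximation for SH at 30 per 100 patient-years:

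- Poisson: ln(30/25.35) = 0.168; SE = √[(1/0.30)/1,547] = 0.0464; 0.168/0.0464 − 1.96 = 1.67, power 95%.
- k=1: SE = √[(1/0.30 + 1)/1,547] = 0.0529; power 89%.

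Simulation (6,000 studies per scenario) gives the values used below. For reading (b), the person probability is 1 − exp(−0.30) = 25.9% under Poisson and 1 − 1/1.30 = 23.1% at k=1.

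| True rate per 100 PY | Events | Reading (b) | Robust rate test |
|---|---|---|---|
| SH 30 | Poisson | 7% | 94% |
| SH 30 | k=1 | <0.1% (declared lower 54%) | 87% |
| DKA 14 | Poisson | 69% | 92% |
| DKA 14 | k=1 | 33% | 89% |

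**Same data, different answers.**

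- 392 SH events in 346 of 1,547 persons (the Poisson expectation at the benchmark): p = 1.0 by (a) and (c), p = 0.007 and lower by (b).
- 427 SH events: p = 0.044 and higher by (a), p = 0.078 by (c).
- Illustrative, 1,354 patient-years with 390 SH events in 300 persons: significantly higher by (a), p = 0.004; significantly lower by (b), p = 0.007.

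**The case against.** The strongest reply is that Determination of Sample Size promises a fuller SAP before any data are tabulated, and trial units and repeat events are normal SAP content. That SAP is not in the documents, so the missing unit is shown only for the text supplied. But the protocol already names the test twice, and it does not fit the endpoint. A later SAP would have to contradict the protocol or pick a unit.

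Second, the largest figures come from reading (b), the one furthest from the Primary Outcome wording, and they require a benchmark that counts repeat events. That is a fair condition. The documents do say events per 100 patient-years, but how the source study counted cannot be seen.

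Third, under the event-count readings without clustering the effect is modest, and no document supports a particular k. This stands. The 8.6% and 6.1% need no clustering; the higher sizes under (a) and (c) do.

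Fourth, reading (a) errs partly towards caution. Its upper tail is 4.3% (SH) and 3.1% (DKA) against 2.5%, and it flags SH at 30 per 100 patient-years 96% of the time against 94% for the robust test. This also stands, though part of that 96% is bought by the inflated size, and the lower tail is inflated too.

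Two further points are true but separate: the Study Endpoints section calls the endpoint a composite, and the literature rate is treated as known without error.

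**Conclusion.** The concern holds. The named test does not match the endpoint, and the undefined trial changes both its size and its conclusion. For SH, the chance of a false significant result at a nominal 5% runs from 5.2% (patient-months) through 8.6% (patient-years) to 77% (persons against an event rate) with Poisson events. For DKA the effect is milder: 5.1%, 6.1% and about 10%. Clustering raises the event-count figures further, by an amount that depends on an assumed k. The person-level figures hold only if the benchmark counts repeat events. All figures assume 1,547 subjects with a full year each. Because this is the primary safety comparison, it should be corrected before the analysis.

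**What to change.** In the Synopsis and in Statistical Analysis:

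1. Replace the binomial test with a one-sample rate test counting all events, for SH and for DKA: intercept-only Poisson regression, offset log(patient-years), robust variance, against the benchmark rate. Negative binomial is an alternative. Take events and patient-years over the same observation period.
2. Replace the two risk-ratio phrases with the rate per 100 patient-years and the observed/expected rate ratio and rate difference, each with a 95% CI.
3. State whether the benchmark counts all events or persons affected.
4. Restate the power in Steps 1 and 2 under this test, giving the alternative rate and assumed dispersion, without changing enrolment.

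In simulation the robust test holds its size: 4.6–5.5% at 1,547 subjects; 4.6–5.9% with 2,063 enrolled and 25% leaving at uniformly spread times (assumed); 4.3–5.5% in the age groups (288 aged 6–13; 246 aged 14–18, i.e. 328 less 25%).

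The cost is wording and a standard model on data already collected. Intervals may widen and the stated power may fall. If 1,354 was sized for 80% power by a one-sample binomial, the implied SH alternatives are about 28.7 or 22.1 per 100 patient-years. An exact Poisson test at 1,354 has 65% or 68% power there and needs about 1,853 or 1,765 patient-years for 80%. For DKA at 1,282 the power is 73% or 76%, and about 1,440 patient-years are needed. Planned enrolment could supply 2,063 × (0.75 + 0.25 × 0.5) = 1,805 patient-years under uniform dropout, so without clustering SH power would be near 80%. With clustering it would be lower.
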